An Audio Music Self-management to Improve ART Adherence in Rural Georgia
IRB#00055077

An Audio Music Self-management to Improve ART Adherence in Rural Georgia

Protocol Dated 03/04/2016

NCT01786148

An Audio Music Self-management to Improve ART Adherence in Rural Georgia

Protocol

[name], [name], [name], [name], [name]

Sponsor: National Institute of Nursing Research/National Institute of Health

July 14, 2012

Updated October 21, 2013

Updated February 8, 2015

Updated August 11, 2015

Updated February 11, 2016

Updated March 4, 2016

Background

a. Specific Aims:

The project has three primary aims and two exploratory aims.

1.0 Revise and adapt the Live Network (LN) program and manual for rural persons living with HIV/AIDS (PLWHA) and develop into a mobile application.

2.0 Conduct a randomized controlled trial to test the efficacy of the program. When compared with an educational music control condition at 3, 6, and 9 months post-baseline, those randomized to the LN will have:

H1: Significantly higher mean antiretroviral therapy (ART) adherence rates (measured by pill counts, self report).

H2: Significantly higher mean levels of ART drug levels in hair sample analyses.

H3: Significantly better clinical indicators: higher mean CD4 lymphocyte counts and percents, a larger proportion achieving virologic suppression (proportion with HIV RNA PCR <50 copies/ml), and smaller proportion with evidence of drug resistance, all as measured by medical record review.

3.0 Explore: a) the effects of LN on symptoms and symptom management; b) the roles of self-efficacy, outcome expectancies, and personal goal setting as mediators, and depression and health literacy as moderators of adherence

4.0 Evaluate the acceptance and adoption of the LN and educational program (EP) mobile application software (app) by examining: a) the antecedent influences of performance expectancy, effort expectancy and hedonic motivation on the behavioral intent-to-use and usage (frequency and duration) of the LN and EP mobile apps; and b) the moderating effects of electronic health (eHealth) literacy and smartphone experience on behavioral intent and subsequent LN/EP mobile app usage.

H1: Performance expectancy, effort expectancy, and hedonic motivation have direct, positive associations with behavioral intent to use the LN/EP mobile apps.

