The target sample size is 200 participants with 100 allocated to each group. Taking into account projected attrition of about 40 persons, we expect a final sample size of 240. Given our approach using multi-level longitudinal models (MLM) for these 200 subjects, 2 groups at 4 time points, we are 95% confident that power levels between 84% to 98% will achieve minimal detectable differences of 0.4 (within time and group by time) and 0.5 (between groups) (small-to-moderate effect sizes) for random effects subjects variance equal to 1. Covariate adjustments should further reduce variability and detectable effect sizes while increasing power. Additionally, to address the differences in proportion achieving virologic suppression and drug resistance, a chi-square test for a sample size of 200 yields a small-to moderate effect size (ω) of 0.1981 for 1 degree of freedom (2 x 2 table) at 80% power and 5% level of significance.

h.2 Plans for data management and analysis

h.2.a Data management Procedures for data management and monitoring will be initiated during the start-up phase. The project coordinator will coordinate the organization and processing of forms, and schedule and implement checks of data quality and completeness. Data from the ACASI files will be saved in the QDS data warehouse. Data will be backed up on a regular basis to prevent loss of data. Data will be transferred electronically from the sites to a secure password protected, HIPAA-compliant server at Emory University. A data-checking plan based on each questionnaire will be used to look for suspicious entries. Data monitoring will include scheduled checks for completeness every 2-4 weeks. Data sets from all assessment points will be merged as necessary to answer the research questions. Personal goals will be reported by the participant and typed into the database for qualitative analysis. They will be analyzed for the dimensions of content, specificity, effectiveness, and control. [name] will oversee the final quality assurance/quality control data reviews. She will design and conduct the statistical analyses; assist as with designing research forms and data entry; and collaborate with the

investigators on analysis and interpretation. We have successfully used these procedures with the pilot project and other research projects.

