h.2.b Analysis Initial analysis will include descriptive statistics of sample characteristics (demographics, substance use, depression scores, etc. and CD4 and Viral Load.) and psychometric evaluation of all scored instruments. A combination of statistical software will be used for statistical analysis and data visualization, including SPSS (v.19), SAS (v. 9.2), and R (v. 2.13). Distributions, potential outliers, and patterns of missing data will be assessed to assure that the data meet assumptions for subsequent inferential tests. Missing data imputation methods may be used for small amounts (<5%) of missing data such that missing data are random. All statistical tests will be performed at the 5% level of significance, with exact p-values reported. Intent-to-treat procedures will be employed. For non-normal data, transformations may be performed to improve deviations from normality. However, it is well known that PC, viral loads and adherence measures are often skewed and experience floor and/or ceiling effects. Therefore, generalized linear models (GLM)/generalized estimating equations (GEE) frameworks will be employed as a more accurate reflection of the true underlying distributions generating these data. It is expected that logistic (logit)³⁷ and log-gamma³⁸ may be appropriate as well as Poisson, zero-inflated Poisson, and other link functions.^{39, 40} Additionally, it is expected that some attrition over time will occur. Mixed/multi-level models (MLM) will be used instead of repeated measures analysis of variance (RM-ANOVA) methods since MLM uses all available data (does not delete cases with missing values over time), handles data that are missing at random (MAR) which RM-ANOVA cannot, does not assume independence across time, provides a breakdown of variance both within and between subjects, and allows for both time-invariant and time-varying covariates.^{39, 40} It is expected that the majority of the analyses will occur in SPSS. However additional MLM and GLM/GEE models will be run using SAS (PROC MIXED, PROC NLINMIXED) and R (packages: LME4, GAMLSS as well as BRugs, which employs Bayesian estimation methods.⁴¹⁻⁴³

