Satisfaction (Aim 1) Two assessments will be conducted and analyzed to determine participant satisfaction with the mobile app in general, LN program and interactive manual. Both times, we will ask questions about likeability, usage rates, ease of use, acceptability, satisfaction, relevance, favorite song, understandability, and suggestions for improvement. The first assessment will entail observations and discussions with rural PLWHA while using the mobile app in focus group format. Observations and discussions will be recorded and content analyzed for themes, which will inform final revisions to the LN app. The second feasibility analysis will be the Program Evaluation Survey at the end of the study. Scaled responses to questions related to the above criteria will be analyzed using descriptive statistics and written comments will be entered into nVivo software and content analyzed for themes. We will also describe and evaluate the usage data from the web application designed to track app usage. We will determine average usage patterns and compare between groups (LN vs. EP).

Outcomes (Aim 2) All covariates will be evaluated to determine if any differences exist at baseline between the 2 groups (LN and EP), as well as testing for interactions (moderation) between groups and time. Inter-correlation among the covariates will also be evaluated. Multicollinearity diagnostics (variance inflation factors, tolerance, condition index) will be used to determine which covariates should remain in the subsequent models. MLM longitudinal models as detailed above will be used for each outcome (H1: adherence, H2: drug levels, and H3: CD4, viral load, drug resistance) to test differences between the 2 groups (group main effect), test for changes/differences from baseline to 3, 6 and 9 month (time main effect) and test for group by time effects (i.e. changes from baseline that are differences between the 2 groups) adjusting for significant covariates/moderators as needed. Appropriate link functions (e.g. logit, Poisson, other) will be assessed for each outcome within the MLM.

Exploratory outcome, mediators and moderators (Aim 3) Symptoms and symptom management scores will be examined using MLM as described above. Self-efficacy, outcome expectancy and personal goals are mediators in our model and meet the criteria for mediators as defined by Baron and Kenny⁴⁴

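### Aim 2 lists two between-arm tests without saying which decides H1–H3, uses baseline at best by subtraction, and lets the data choose the covariates

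*Combined protocol and SAP*

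**What the plan says.** **Hypotheses.** Specific Aims, Aim 2.0, introduces H1–H3 with "When compared with an educational music control condition at 3, 6, and 9 months post-baseline, those randomized to the LN will have", followed by better results on each outcome. No deciding visit, average or joint test is named.

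**Tests.** In h.2.b, Outcomes (Aim 2), a multilevel longitudinal model for each outcome will "test differences between the 2 groups (group main effect), test for changes/differences from baseline to 3, 6 and 9 month (time main effect"), and then "test for group by time effects (i.e. changes from baseline that are differences between the 2 groups) adjusting for significant covariates/moderators as needed". The time effect does not compare the arms; the other two terms do.

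**Power.** Section h.1 sizes a model with "2 groups at 4 time points", so baseline is one of the modelled visits. It gives detectable differences of 0.4 for group by time and 0.5 between groups, with power of 84–98%, and ranks neither test.

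**Level.** "All statistical tests will be performed at the 5% level of significance" (h.2.b). No multiplicity rule follows.

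**Covariates.** "All covariates will be evaluated to determine if any differences exist at baseline between the 2 groups (LN and EP"). Then: "Multicollinearity diagnostics (variance inflation factors, tolerance, condition index) will be used to determine which covariates should remain in the subsequent models". What remains is adjusted for if significant and if needed. No Aim 2 covariate list is given. Depression and health literacy are named as moderators for Aim 3, and age and gender as covariates for Aim 4. Nothing says that the baseline outcome is a covariate, or that the arms are modelled with a common baseline mean.

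**The concern.** The two between-arm terms answer different questions. If the group main effect is averaged over all four visits, it includes a visit at which treatment cannot yet have acted. If the model is coded with baseline as the reference visit, the group term is simply the baseline difference and carries no treatment effect. The plan does not state the coding. Group by time does target the treatment effect, but as a change from baseline, which is usually less precise than adjusting for baseline.

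The choice can change the conclusion. Suppose there is no treatment effect, total SD is 1, the correlation between visits is 0.5, and LN happens to start 0.2 higher. The visit-averaged main effect is then expected to be 0.2 × (0.25 + 0.75 × 0.5) = +0.125, and the change contrast 0.2 × (0.5 − 1) = −0.10. The two tests are pushed in opposite directions.

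Three things are at stake: a diluted estimate if the main effect is reported, unused precision if group by time is reported, and a larger false-positive rate if the choice is made after seeing both. Choosing covariates by significance adds further freedom.

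**Working it through.** **Inputs from the documents:** 100 per arm, 4 visits and subject variance 1 (h.1); 5% per test (h.2.b).

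**Assumed:** continuous outcome, compound symmetry, two-sided tests, and residual variance r, which the plan does not give.

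**1. The plan's own figures.** The chi-square effect size reproduces: (1.960 + 0.842)/√200 = 0.1981. So does enrolment: 200 + 40 = 240. The 84–98% for the longitudinal model cannot be checked without r. As r runs from 0.25 to 2, power for 0.5 between groups runs from 92.9% to 82.3%. Power for a constant 0.4 on the 3-df group-by-time test runs from 99.1% to 27.5%. I use r = 0.50 and r = 0.2875 (0.29 when rounded) because they give that 3-df test 84% and 98%. Assigning both ends of the range to this test is my assumption.

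**2. Dilution of the main effect.** An effect d at months 3, 6 and 9 only averages to (0 + d + d + d)/4 = 0.75d. The variance is (2/n)(1 + r/4).
- r = 0.50: SE = √(0.02 × 1.125) = 0.150. For 0.5, z = 3.33 and power is 91.5%. For 0.375, z = 2.50 and power is 70.5%.
- r = 0.2875: SE = 0.1464. Power is 92.7% and 72.6%.

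The factor depends on which occasions are modelled. With a baseline and nine monthly pill counts (assumed) it would be 9/10 = 0.9.

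**3. Precision of group by time.** For the three arm contrasts, the covariance is Vc = (2r/n)(I + J) with baseline subtracted, and Va = (2r/n)(I + J/(1 + r)) with baseline conditioned on or arm means held equal at baseline. The noncentrality is λ = d′V⁻¹d on 3 df. For a constant d, λc = (n d²/2r) × 0.75 and λa = (n d²/2r) × 3/(1 + 3/(1 + r)).

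| r | d | λc | λa | Power, subtracted | Power, conditioned | λ ratio |
|---|---|---|---|---|---|---|
| 0.50 | 0.4 | 12.0 | 16.0 | 84.0% | 93.4% | 1.33 |
| 0.2875 | 0.4 | 20.9 | 25.1 | 98.0% | 99.3% | 1.20 |
| 0.50 | 0.5 | 18.75 | 25.0 | 96.6% | 99.3% | 1.33 |

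**4. Effect pattern.** For effects 0, 0.25 and 0.75 at r = 1, the planned 3-df test has 96.6% power, its common-baseline version 98.2%, and the baseline-adjusted 3/6/9-month average only 73.3%. At r = 0.5 these are over 99.9%, over 99.9% and 91.5%. The average is therefore not always the best contrast.

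**5. Where the precision gain can fail.** Take baseline SD 0.6, follow-up SD 1 and correlation 0.7 throughout (assumed). The mean of the three follow-ups has variance (1 + 2 × 0.7)/3 = 0.80, and its covariance with baseline is 0.42. For the 3/6/9-month average:
- change from baseline: 0.02 × (0.80 + 0.36 − 0.84) = 0.0064;
- common-baseline, random-intercept model (implied slope 0.56/0.84 = 0.667): 0.02 × (0.80 + 0.16 − 0.56) = 0.0080;
- fitted baseline slope (0.42/0.36 = 1.167): 0.02 × (0.80 − 0.49) = 0.0062.

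The gain needs a fitted baseline slope or an unstructured covariance.

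**6. Error if either test may be claimed.** Under compound symmetry the two tests are independent, so the rate is 1 − 0.95² = 9.75%. Simulation (400,000 null trials at each correlation of 0.3, 0.5 and 0.7) gives 9.7–9.8%. AR(1) correlations of 0.4 and 0.7 give 9.7% and 10.6% (6,000 runs each, SE about 0.4 points). Counting only results that favour LN, the rate is about 4.9% against 2.5%.

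**The case against.** Group, time and group by time are the ordinary terms of one longitudinal model. Group by time is the only one that the plan defines as a between-arm difference in change, and the pilot RCT reported its viral-load result as that interaction. No sentence says that either test suffices. A reader might infer that the trial's error rate is 9.75%. The documents do not support this: the figure applies only if either test is allowed to count, and it includes results in the wrong direction. What stands is that h.1 sizes both tests and no sentence excludes the open choice.

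Subtracting baseline is valid under randomisation, and in the matched cases above the plan already has 84–98% power. A reader might infer that modelling baseline inflates the error of a test, or that conditioning always gains. Neither follows: each test holds 5% on its own, and step 5 shows a case where a common-baseline model loses.

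Much of Aim 2 is not continuous. Section h.2.b itself says "it is well known that PC, viral loads and adherence measures are often skewed and experience floor and/or ceiling effects" and plans non-normal links, while suppression and resistance are binary. The power figures therefore apply to outcomes such as CD4 and perhaps hair levels. The unnamed test and the open covariate choice apply to all.

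A reader might also infer that participants starting ART have no baseline adherence or hair value. The documents do not show this.

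**Conclusion.** The point holds and should be fixed before the data are analysed. On the text alone, no deciding test is named for H1–H3, the plan commits to no adjustment for the baseline outcome, and covariates are selected from the data. These findings need no numerical assumption.

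The sizes do need assumptions. The 0.75 factor needs a main effect averaged over four visits and a constant follow-up effect. The powers rest on compound symmetry, a continuous outcome and an assumed residual variance. The precision gain is useful rather than essential: 84 to 93% at residual 0.50, but only 98 to 99% at 0.29. The 9.75% is two-sided, per outcome, and conditional on either test being claimable. The effect of covariate selection is not sized, and the stated 84–98% power is neither confirmed nor refuted.

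**What to change.** - **Deciding contrast.** For each outcome, name one LN–EP post-baseline contrast: the 3/6/9-month average, a stated visit, or the joint three-visit test. Choose it from the expected pattern. The pilot saw adherence fall in both arms and further in controls, so an effect that grows over time deserves thought. Treat the other terms as supportive.
- **Baseline, roughly continuous outcomes.** Use a follow-up-only model with the baseline outcome as covariate and visit-specific baseline slopes, or a four-visit model with a common baseline mean and unstructured covariance. A random-intercept-only version can lose precision when visit variances differ. Do not enter baseline as both response and covariate.
- **Baseline, binary or skewed outcomes.** Enter the baseline value as a covariate with the planned link, without claiming the power figures above.
- **Covariates.** Replace the significance-driven rule with a short fixed list kept whatever its p-values, for example site and ART entry route.
- **Missing baseline.** If some participants starting ART have no baseline adherence or hair value, state how they are kept in the analysis.

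The cost is analysis-plan wording and a few degrees of freedom. No new data are needed.

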RCT: Inclusion criteria for the study are: 1) HIV infection; 2) initiating ART for the first time (except women who may have had ART during pregnancy) or changing ART regimen within the past 3 months due to side effects or virologic resistance; or 3) HIV+ individuals with a detectable viral load \geq 40copies/ml; 4) HIV+ individuals on ART medication 5) \geq 18 years of age; 6) English speaking; and 7) willing to complete 4 assessments, monthly unannounced pill counts, and collection of hair samples, be randomly assigned to either condition, and participate in study activities that include using smart phone and mobile app. Persons will be excluded from the study if they are not HIV infected, homeless, are a minor under 18 years of age and therefore unable to give independent informed consent, are unable to read or understand English since all of the questionnaires and the audio program and manual will be in English, have a history of or self-report bilateral hearing loss, cognitive impairment (inability to comprehend the informed consent document), are actively psychotic, severely depressed/suicidal, or pose a risk of harm to themselves or others (Brief Symptom Inventory; BSI), since these persons may not be capable of using the mobile app or completing the assessments. Depending on the severity, these persons will be walked to or referred to the mental health counselor, once the mental health issues have been addressed, they may be re-screened for eligibility. Substance users will not be excluded from the study, except if they display the above mentioned mental health characteristics or pose a risk of harm to themselves or others.

b. Setting

The study sites are within 5 health district sites that provide care to HIV+ persons in rural counties in Georgia outside the 20-county Metropolitan Atlanta Statistical area (MSA). The sites of the project are:

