District 5-2 North Central (Macon) is located in the central portion of the state. In 2012, there were 2802 persons living with HIV/AIDS in this district. The Hope Center provides the bulk of HIV care to persons living in the 13 counties that comprise District 5-2. The clinic offers a broad array of HIV health services: primary care, HIV maintenance care, pharmacy, laboratory, vision, and dental. Case management, nutritional counseling, community support, and mental health services are also available. From January 1 to Aug 2, 2011, the clinic reported a caseload of 776 clients. 61.5% of these individuals were male; 82% were African Americans; and 74% lived at or below the federal poverty level. Currently there are 647 persons on ART, about 150 people were started on ART, and 100 changed existing medication regimens in the previous year.

District 6 East Central (Augusta) is located in the east central portion of the state. In 2009 there were 2540 persons living with HIV/AIDS in the district. The only site for HIV care in this area is at the Georgia Health Sciences University. The infectious disease clinic serves persons from the 13 counties in District 6 as well as two South Carolina counties (Aiken and Edgefield). 11 of the Georgia counties and Edgefield County, SC, have less than 35,000 people, meeting the US Census Bureau definition of 'rural'. 10 Georgia counties are designated as Medically Underserved Areas (MUA), three are designated as having Medically Underserved Populations (MUP); and 12 meet the criteria for Primary Health Professional Shortage Areas (HPSA's). The infectious disease clinic has 1314 patients and about 70% are African American and 71% are at or below the federal poverty level. The clinic provides comprehensive primary care to HIV infected persons including pharmaceutical assistance, nutrition services, mental health and substance abuse services, and dental services. There are about 12 new patients a month, and 83% of all patients are on ART.

District 9-1 Coastal (Brunswick) is located on the southeastern coast of Georgia. There are five HIV care clinics serving people in 12 counties. In 2009 there were 2829 persons living with HIV/AIDS in the district, the largest outside the 20-county metropolitan Atlanta area. Ten counties are rural; seven of the counties are designated MUA and seven are HPSA. The clinics serve about 1100 clients, 75% of

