RCT: Sources of information will include baseline, 3, 6, and 9- month follow-up assessments and tracking of usage of mobile app conducted solely for the purpose of this research. Assessments will include assessments of adherence to antiretroviral medications and, measures of symptoms, depression, self-efficacy, attitudes, goals, demographic information including substance use, and health literacy. Physiologic measures will include ART drug levels in a small hair sample (100 strands) cut from the occiput (back of head) at each time point. Lab results for CD4, viral load, and drug resistance will be extracted from medical records consistent with the study time points. Study assessments will be conducted in person using ACASI coincident with provider appointments. They will last about 3 hours. Monthly unannounced pill counts will be conducted via smart phone using the camera and pill count survey within app with assistance from the clinical research coordinator as needed. As part of our reliability testing, up to 60 participants will be asked to repeat their pill count about 24 hours after baseline. Hair samples will be collected in person by study personnel on-site at each time point. Tracking usage of the app will be done via the mobile web application which will send messages to the HIPAA compliant server each time a participant uses the app. Participants will be assigned to one of two conditions: an educational music program (EP) or the LN treatment condition. All participants will receive the usual care at their respective HIV care agencies. Evaluation information will be obtained about the satisfaction and use of the programs at the end of the RCT study. The option of 3, 6, and 9 month follow up study assessments administered via phone call will be offered to participants who are unable to complete in person visits. If this option is elected the hair sample and visual analog scale data will not be collected.

d.1.b Other interactions

Participants will receive reminder calls and text messages regarding study appointments. Text messages will also remind them to listen to the LN & EP.

d.2 Respondent burden

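### Aim 2 states H1 and H2 as follow-up levels, but the listed tests bring in a baseline that has no clear meaning for first-time ART starters, and no deciding test is named

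*Combined protocol and SAP*

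**What the plan says.** Section a, Specific Aims, introduces the Aim 2 hypotheses with "When compared with an educational music control condition at 3, 6, and 9 months post-baseline, those randomized to the LN will have". H1 reads "Significantly higher mean antiretroviral therapy (ART) adherence rates (measured by pill counts, self report", and H2 is worded the same way for hair drug levels. Both concern levels at follow-up.

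Section h.2.b, Outcomes (Aim 2), fits one longitudinal model per outcome and lists three tests:
- group: "to test differences between the 2 groups (group main effect"
- time: "test for changes/differences from baseline to 3, 6 and 9 month (time main effect"
- group by time: "test for group by time effects (i.e. changes from baseline that are differences between the 2 groups"

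It does not say which of these decides H1 or H2.

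The RCT criteria in section a.2 admit people "initiating ART for the first time (except women who may have had ART during pregnancy", along with regimen changers, people with a detectable viral load and people on ART. Section d.2.1 takes hair at every time point. It also implies a baseline pill count, since up to 60 participants are "asked to repeat their pill count about 24 hours after baseline". No section says what baseline adherence or baseline hair level means for a first-time starter.

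**The concern.** A person who has taken no ART has no adherence rate. Their hair, if sampled before the first dose, would be expected to show no drug. For such a person, change from baseline is either undefined (H1) or largely a record of having started therapy (H2).

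The missing-data text in h.2.b does not cover this. It relies on data being missing at random and allows imputation for less than 5% missing, whereas this value is absent by design. Whether to code it as 0, as 100 or as missing is left to the analyst, on the main efficacy hypotheses.

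Neither group comparison matches the hypotheses as worded. The group-by-time test subtracts a baseline difference between arms that randomisation already makes zero in expectation. The main effect averages in a visit at which no effect can exist.

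**Working it through.** **The plan's own figures (h.1).** The chi-square effect size reproduces: √((1.96 + 0.8416)² / 200) = 0.1981. So does the enrolment target: 200 + 40 = 240. The 84-98% power range for the longitudinal model cannot be reproduced uniquely, because residual variance and within-person correlation are not given. For example, with total variance 1, a 0.4 change from baseline to one visit has 66.7%, 80.7% and 95.5% power at correlation 0.3, 0.5 and 0.7. The range assumes four time points for all 200 participants.

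**Share of starters.** The protocol gives no projection. Clinic flow in section b, Setting, gives only the mix of starters and changers:
- Macon: "about 150 people were started on ART, and 100 changed existing medication regimens in the previous year", so 150 / (150 + 100) = 60% starters.
- Athens: 50% of 35 new patients in 7 months is 17.5, or 2.5 a month, against 5-8 changes a month. That is 2.5 / 10.5 = 24% to 2.5 / 7.5 = 33%.

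The wider eligibility may lower these shares, so a range of 0 to 60% is used.

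**Assumptions.** n = 100 per arm (h.1). Total SD 1, equal correlation ρ between visits, an effect of 0.4 SD at each follow-up visit and none at baseline, two-sided 5%. A share s has no usable baseline. Power = Φ(effect / SE − 1.96).

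**Formulas.** Let A = (1 + 2ρ)/3, the variance of one person's three-visit mean, and β = ρ/A.
- Group by time (mean follow-up minus baseline, all available data): SE² = (2/n) [A(1 − β)² + (1 − ρ²/A)/(1 − s)]; effect 0.4.
- Group main effect, taken as the equally weighted four-visit mean: SE² = (2/n) [A(3 + β)²/16 + (1 − ρ²/A)/(16(1 − s))]; effect (0 + 3 × 0.4)/4 = 0.3.
- Unadjusted follow-up mean: SE² = 2A/n; effect 0.4.
- Proposed analysis (follow-up mean, entry route, baseline as covariate where it exists): SE² = (2/n) [sA + (1 − s)(A − ρ²)]; effect 0.4.

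**Worked case, ρ = 0.5, s = 0.6.** A = 0.667 and β = 0.75.
- Group by time: SE² = 0.02 × (0.0417 + 0.625/0.4) = 0.0321, SE 0.179, power 61%.
- Proposed: SE² = 0.02 × (0.6 × 0.667 + 0.4 × 0.417) = 0.0113, SE 0.106, power 96%.

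**Power (%) at s = 0 / 25% / 40% / 60%**

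| ρ | Group by time | Four-visit main effect | Unadjusted follow-up | Proposed |
|---|---|---|---|---|
| 0.3 | 83 / 73 / 64 / 48 | 87 / 86 / 84 / 81 | 97 | 99 / 99 / 98 / 98 |
| 0.5 | 93 / 86 / 78 / 61 | 77 / 76 / 75 / 73 | 93 | 99 / 98 / 98 / 96 |
| 0.7 | 99 / 97 / 94 / 81 | 67 / 67 / 66 / 65 | 89 | 100 / 99 / 98 / 95 |

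**Hair as a floor value (H2).** If starters' baseline hair is kept as a constant floor and entry route is adjusted for, the change score has SE² = (2/n) [sA + (1 − s)(4/3)(1 − ρ)]. As s goes from 0 to 60%, power is 83-92% at ρ = 0.3, 93% at 0.5 and 99-94% at 0.7.

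**The case against.** The case for the plan has real force, and several stronger readings fail.

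- A reader might infer that H1 and H2 rest only on change from baseline. They do not: a group main effect is also listed, and the hypotheses are worded as levels. But that main effect includes the baseline visit and is not named as deciding.
- A reader might infer that most participants lack a baseline. The 60% is Macon's ratio of starters to starters plus changers. Athens gives 24-33%, and people on ART are also mentioned in the criteria. Initiating may also include people who began ART in the past 3 months and so have some adherence to measure. The pilot enrolled people who had started or changed ART within 6 months, and compared 21 + 42 = 63 of them with baseline.
- A reader might treat starters' hair baseline as missing. It can be sampled and assayed, and an expected floor reading is an observation. The loss for H2 is then smaller.
- A reader might say that a baseline pill count covers no interval. The instruments are filed separately, so the scoring cannot be judged here, and H1 also uses self-report.
- A reader might infer bias between arms. None is shown: starters are randomised, and the mixed model keeps people without a baseline.
- Dropping baseline altogether is not always better. At ρ = 0.7 with 25% lacking it, group by time has 97% power against 89% for the unadjusted follow-up mean. At ρ = 0.3 the gap of 83% against 97% exists even with complete baselines, so part of it comes from change scoring and not from starters.

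The last point argues for keeping baseline as a covariate where it exists. It does not rescue the listed tests: in every cell of the table the proposed analysis has at least as much power as either of them.

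**Conclusion.** The concern holds in this form: for H1 and H2 the plan names no deciding contrast, neither listed group comparison matches the follow-up comparison that Aim 2 states, and baseline is left undefined for an eligible subgroup. The consequence is lost precision and an unclear estimate.

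Under the stated assumptions, power is 48-99% for group by time and 65-87% for the four-visit main effect, against 95-100% for the proposed analysis. For H2 with a floor baseline, the change score keeps 83-99%.

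These figures depend on the starter share and the correlation, neither of which the documents give. They also depend on a continuous, equal-variance approximation, while h.2.b expects skewed outcomes and other link functions. The ordering of the methods is more secure than any single percentage. This should be changed before analysis, but it does not threaten the trial's validity.

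**What to change.** For H1 and H2, name the LN-EP difference in the 3, 6 and 9 month values as the deciding contrast, first averaged over the three visits and then by visit. Fit the model to the follow-up values only. Include:
- entry route (starter or already on ART) as a fixed covariate;
- the baseline value as a covariate for on-ART participants only, entered as value × on-ART indicator.

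State how a starter is identified relative to the baseline visit, and report the number by arm. Starters' baseline hair readings can be described but should not enter a change score.

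For CD4 and continuous viral load, the baseline value can likewise be a covariate in place of change scores.

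The cost is SAP wording only. No new data are needed, because entry criteria are already held in the site tracking log (h.2.b, Aim 5).
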